### 3.4 Duration of Therapy

Patients may receive up to 2 cycles of therapy prior to surgery. Surgery must occur within 14 days of final scans. Patients will continue the study drug following final scans and then discontinue the study drug between 3 and 7 days prior to surgery, and thus may ultimately receive up to two weeks additional therapy with study drug beyond end of cycle 1 (or cycle 2) while awaiting surgery. No treatment with the study drug will be given after surgery.

Criteria for treatment with Cycle #2:

- No Grade 3 or higher AEs with Cycle #1
- No evidence of PD by RECIST 1.1 criteria at end of Cycle #1 scan.
- Additional reduction in tumor size deemed to be potentially beneficial by thoracic surgeon planning to perform resection.

Treatment may be stopped for any of the following reasons:

- The patient or legally authorized representative withdraws consent.
- Any AE that in the opinion of the investigator would pose an unacceptable safety risk to the patient.
- Closure of the study.

### 3.5 Duration of Follow Up

Patients will be followed for safety assessments 30 days following the Day 15 post-operative visit, or removal from study, or until death, whichever occurs first. Patients removed from study for unacceptable treatment-related AE(s) will be followed until resolution or stabilization of all treatment related AEs to Grade 2 or lower. Patients whose disease is not resectable at the time of scheduled surgery will be managed per standard of care for patients with unresectable EGFR-mutant NSCLC. All patients will be followed for disease relapse and OS for up to 5 years.

### 3.6 Randomization Procedures

There is no randomization in this study.

### 3.7 Study Timeline

#### 3.7.1 Primary Completion

Accrual in this study is expected to require 36 months. Data collection will be complete 60 months after enrollment of the last patient.

### 3.7.2 Study Completion

In total, this study is expected to reach completion approximately 96 months from the time accrual opens.

## 4 Study Drugs

### 4.1 Description, Supply and Storage of Investigational Drugs

#### 4.1.1 Osimertinib

Osimertinib is provided as beige, film-coated tablets, containing either 40 or 80 mg osimertinib expressed as a free base. Osimertinib tablets are packed in high-density polyethylene bottles with desiccant, sealed with a child-resistant closure and induction-sealed membranes.

Osimertinib tablets contain osimertinib mesylate, mannitol, microcrystalline cellulose, low-substituted hydroxypropyl cellulose and sodium stearyl fumarate. The tablet film-coat contains polyvinyl alcohol, titanium dioxide, polyethylene glycol 3350, talc, yellow iron oxide, red iron oxide and black iron oxide.

#### Classification

Osimertinib is a small molecule EGFR TKI, FDA-approved for patients with metastatic EGFR-mutated NSCLC with a T790M mutation, who have progressed on prior EFR TKI therapy.

#### Mechanism of Action

Irreversible EGFR TKI for specific mutated forms of EGFR, including T790M, L858R, and exon 19 deletion. Biochemical studies showed osimertinib to be a potent and selective inhibitor of mutant EGFRs binding at approximately 9-fold lower concentrations as compared to wild-type EGFR (IC50 of 12 nM for mutant EGFR and 185 nM for wild-type). In a screen against 265 other protein kinase, osimertinib had significant activity, as defined by >60% inhibition at 1nM, against only 18 other kinases, including ACK1, BLK, ErbB2, ErbB4, BRK, MLK1, and MNK2. In cellular assays, osimertinib potently inhibited both EGFR-mutant cell lines and cell lines bearing an additional T790M mutation (IC50 6 nM to 54nM), with weaker inhibition of wild-type EGFR cell lines (IC50 480 nM to 1.8 μ). This correlated with reduced cell proliferation upon osimertinib exposure and to tumor regression in EGFR-mutant mice bearing xenograft tumors both with and without the T790M mutation. Tumor regression was accompanied by pharmacodynamic inhibition of pEGFR and downstream biomarkers pAKT and pERK.

#### Metabolism

PKs were linear over a 20 to 240 mg dose range and steady state is reached at approximately 15 days treatment. Osimertinib showed a high volume of distribution and is predicted to bind plasma proteins. The mean half-life of osimertinib was 48 hours. In animal studies, tissue distribution was widespread, with highest concentrations at the uvea and retinal pigment epithelium, renal cortex, pituitary, spleen, bile ducts, lung, and Hadarian gland.

Metabolism is primarily via the CYP3A4/5. Two pharmacologically active metabolites (AZ7550 and AZ5104) are generated with similar kinase selectivity and accounted for less than 10% of exposure compared to osimertinib. Renal clearance accounts for less than 1% of overall clearance. Excretion is primarily fecal (68%), with minor urinary excretion (14%). PKs have been studied in patients with moderate renal impairment (CrCl 30-59 mL/min) and with mild hepatic impairment (AST greater than ULN with normal bilirubin, or total bilirubin 1-1.5xULN with any AST). PKs in patients with more severe renal or hepatic impairment are unknown.

## Contraindications

The use of any natural/herbal products or other “folk remedies” should be discouraged, but use of these products, as well as use of all vitamins, nutritional supplements, and all other concomitant medications must be recorded in the electronic case report form (eCRF).

## **Drugs That May Prolong QT Interval**

The drugs listed in this section are taken from information provided by The Arizona Center for Education and Research on Therapeutics website: <https://www.crediblemeds.org/>. The website categorizes drugs based on the risk of inducing Torsades de Pointes (TdP).

During screening the drugs that patients are currently prescribed should be checked opposite the ArizonaCert website.

## **Drugs with a known risk of Torsades de Pointes**

The following drugs prolong the QT interval and are clearly associated with a known risk of TdP, even when taken as recommended. These drugs must have been discontinued prior to the start of administration of study treatment in accordance with guidance provided in Table 3 and should not be co-administered with study treatment (osimertinib) and for a period of two weeks after discontinuing study treatment. **The list of drugs may not be exhaustive and is subject to change as new information becomes available. As such, investigators are recommended to search the website to provide the most up to date information.**

**Table 4.1 Drugs prolonging the QT interval**

Contraindicated drug	Withdrawal period prior to osimertinib start
Clarithromycin, droperidol, erythromycin, procainamide, aclarubicin, anagrelide, ciprofloxacin, cocaine, levofloxacin, ondansetron, papaverine hydrochloride, sulpiride, sultropride, terfenadine terlipressin	2 days
Cisapride, disopyramide, dofetilide, domperidone, ibutilide, quinidine, sotalol, sparfloxacin, thioridazine	7 days
Bepidil, chlorpromazine, halofantrine, haloperidol, mesoridazine	14 days
Levomethadyl, methadone, pimozide	4 weeks
Arsenic trioxide	6 weeks*
Pentamidine	8 weeks
Amiodarone, chloroquine	1 year

\*Estimated value as PKs of arsenic trioxide has not been studied

Metabolism of osimertinib is primarily carried out by CYP3A4/5. A drug-drug interaction study of osimertinib evaluated in patients showed that there is potential for osimertinib being a victim when co-administered with strong inducers of CYP3A4 (osimertinib concentrations are decreased when co-dosed with rifampicin)

The following potent inducers of CYP3A4 must not be used during this study for any patient receiving osimertinib.

**Table 4.2 Drugs inducing CYP3A4**

Contraindicated drugs	Withdrawal period prior to osimertinib start
Carbamazepine, phenobarbital, phenytoin, rifampicin, rifabutin, rifapentine	3 weeks
St John's Wort	
Phenobarbitone	5 weeks

This list is not intended to be exhaustive, and a similar restriction will apply to other agents that are known to strongly modulate CYP3A4 activity. Appropriate medical judgment is required.

Osimertinib and its metabolites are substrates for P-gp and BCRP. Osimertinib may increase the concentration of sensitive BCRP and Pgp substrates (concentration of the sensitive BCRP substrate, rosuvastatin and sensitive Pgp substrate, fexofenadine, are increased).

**Table 4.3 Exposure may be increased by osimertinib treatment**

Warning of possible interaction	Advice
Rosuvastatin	Drugs are permitted but caution should be exercised and patients monitored closely for possible drug interactions. Please refer to full prescribing information for all drugs prior to co-administration with osimertinib.
Sulfasalazine	
Doxorubicin	
Daunorubicin	
Topotecan	
Dabigatran	
Aliskiren	
Digoxin	

With the exception of contraindicated drugs listed above, therapies considered necessary for the patient's well-being may be given at the discretion of the investigator and should be documented on the eCRF. Other concomitant medications, except for analgesics, chronic treatments for concomitant medical conditions, or agents required for life-threatening medical problems, should be avoided.

Herbal and complementary therapies are not permitted as potential drug-drug interaction cannot be definitively excluded.

No other anti-cancer therapies (including chemotherapy, radiation, hormonal treatment [except corticosteroids and megestrol acetate], antibody or other immunotherapy or other experimental drugs) of any kind are permitted.

#### Availability

Osimertinib is absorbed orally, with a median time to maximum concentration (Cmax) of 6 hours (range 3-24 hours). Oral bioavailability was similar in the fasting state and following a high-fat meal. Absorption is not affected by gastric pH.

#### Storage and handling

All study drugs should be kept in a secure place under appropriate storage conditions. The IP label on the bottle and the Investigator Brochure specifies the appropriate storage

Osimertinib should be stored in its original packaging at 25°C (77°F); excursions to 15-30°C are permitted.

Side Effects**Table 4.4 Adverse Reactions as Reported in the AURA Studies (Phase II and Phase III) [51]**

Category	Adverse Event	CIOMS Descriptor (Overall Frequency)	Frequency of CTCAE Grade 3 or Higher
Pulmonary	ILD	Common (3.2%)	1.3%
Gastrointestinal	Diarrhea	Very common (44%)	1%
	Stomatitis	Very common (15%)	0%
Ocular	Keratitis	Uncommon (0.9%)	0%
Dermatologic	Rash	Very common (41%)	0.7%
	Dry skin	Very common (29%)	0%
	Paronychia	Very common (27%)	0%
	Pruritus	Very common (15%)	0%
Cardiac	QTc interval prolongation	Uncommon (0.7%)	0.7%
Hematologic	Platelet count decreased	Very common (54%)	2.1%
	Leucocytes decreased	Very common (66%)	2.4%
	Neutrophils decreased	Very common (32%)	4.3%

Complete and updated AE information is available in the Investigational Drug Brochure and product package insert.

**4.2 Drug Accountability**

The Investigational Pharmacist will manage drug accountability records.

**4.3 Drug Ordering**

UCSF will obtain osimertinib directly from AstraZeneca as study supply.

**4.4 Packaging and Labeling of Study Drugs**

Drugs will be packaged and labeled per UCSF institutional standards, adhering to applicable local and federal laws.

**5 Treatment Plan****5.1 Dosage and Administration**

Treatment will be administered on an outpatient basis.

**Table 5.1 Regimen Description**

Study Drug	Premedication; precautions	Dose (mg/day)	Route	Schedule	Cycle Length
Osimertinib 	Can be taken with or without food	80 mg	Oral	Daily	4 weeks (28 days)

Osimertinib is administered as an 80 mg tablet orally once daily. Osimertinib can be taken without regard to food. Osimertinib doses should be taken approximately 24 hours apart at the same time point each day. Doses should not be missed. If a patient misses taking a scheduled dose, within a window of 12 hours, it is acceptable to take the dose. If it is more than 12 hours after the dose time, the missed dose should not be taken, and patients should be instructed to take the next dose at the next scheduled time. If a patient vomits after taking their osimertinib, they should not make up for this dose, but should take the next scheduled dose. Each dose should be taken with 8 oz (240 mL) of water.

The patients will be requested to maintain a medication diary for each dose of medication. The medication will be returned to clinic staff at the end of each cycle. Any change in dosing schedule, dose interruptions, or dose reductions should be recorded.

#### 5.1.1 Other Modalities or Procedures

**Surgery/Anesthesia:** Surgical resection of the patients lung cancer will be carried out in accordance with the institutions standard practice and surgical guidelines. The last dose of study drug prior to surgery will be taken by the study participant between 3 and 7 days prior to surgery. The attending anesthesiologist for the case will be notified and informed of the QTc prolonging potential of the study drug. Drugs that are known to cause or possibly cause QTc prolongation (See [crediblemeds.org](http://crediblemeds.org)) should be avoided. Anesthesiologists should be made aware that this list includes Sevoflurane and Propofol, which should be avoided as anesthetics if possible.

## 5.2 Dose Modifications and Dosing Delays

If a patient experiences a CTCAE grade 3 or higher and/or unacceptable toxicity including a DLT, not attributable to the disease or disease-related processes under investigation, dosing will be interrupted and supportive therapy administered as required in accordance with local practice/guidelines.

If a toxicity resolves or reverts to  $\leq$ CTCAE grade 2 within 3 weeks of onset, treatment with osimertinib may be restarted at the same dose (80 mg) or a lower dose (40 mg) using the rules below for dose modifications (Table 5.2) and with discussion and agreement with Principal Investigator (PI). There will be no individual modifications to dosing schedule in response to toxicity, only potential dose reduction or dose interruption.

On resolution of toxicity within 3 weeks: If an AE subsequently requires dose interruption, osimertinib may restart at the same dose or the reduced dose, on resolution/improvement of the AE at the discretion of the Investigator.

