**Table 5.2 Dose Modifications and Dosing Delays**

Dose Level	Osimertinib (PO daily) Each Cycle 28 Days
0	80 mg
-1	40 mg

Treatment or visit delays for public holidays or weather conditions do not constitute a protocol violation.

The following dose modification rules will be used with respect to potential toxicity. Toxicity will be assessed according to the NCI CTCAE Version 4.03.

If a patient experiences a CTCAE grade 3 or higher and/or unacceptable toxicity including a DLT, not attributable to the disease or disease-related processes under investigation, dosing will be interrupted and supportive therapy administered as required in accordance with local practice/guidelines.

If toxicities do not resolve to less than or equal to Grade 2 after 2 weeks despite supportive care, then the participant should be withdrawn from the study.

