**Table 5.3 Dose Modifications and Dosing Delays Tables for General Adverse Events**

Grade of Event	Management/Next Dose for Osimertinib
≤ Grade 1	No change in dose
Grade 2	Hold until ≤Grade 1 if clinically significant, otherwise no change in dose Resume at same dose level
Grade 3	Hold* until <Grade 2 Resume at one dose level lower, if indicated**
Grade 4	Off protocol therapy

\*Patients requiring a delay of >2 weeks should go off protocol therapy

\*\*Patients who do not tolerate 40 mg PO daily dose will be taken off protocol therapy

\*\*\*Alopecia/hair color changes are excluded from requirement for dose delays or modifications

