## Dose Modifications and Dosing Delays Tables for Specific Adverse Events

**Table 5.4 Adverse Event: Diarrhea**

Grade of Event	Management/Next Dose for Osimertinib
≤ Grade 1	No change in dose
Grade 2	Hold until ≤Grade 1 if clinically significant, otherwise no change in dose Resume at same dose level
Grade 3	Hold* until ≤Grade 2 Resume at one dose level lower**
Grade 4	Off protocol therapy

Recommended management: Loperamide antidiarrheal therapy, see section 5.3.1

\*Patients requiring a delay of >2 weeks should go off protocol therapy

\*\*Patients who do not tolerate 40 mg PO daily dose will be taken off protocol therapy

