**Table 5.5 Adverse Event: Pulmonary/Cardiac Toxicity**

PULMONARY	
Notes:	

 
Withhold osimertinib for acute onset of new or progressive unexplained pulmonary symptoms, such as dyspnea, cough and fever and during diagnostic workup for pneumonitis/ILD.
 
During evaluation of potential grade 2, 3, and 4 pneumonitis, if an infectious etiology is confirmed (i.e., pneumonia) and pneumonitis is excluded, then consider resuming at current dose level after the pneumonia resolves.
 
	
ILD/Pneumonitis	
Grade of Event	Dose Modifications for osimertinib
Grade 1 or greater	Permanently discontinue osimertinib
CARDIAC INVESTIGATIONS	
Abnormal LVEF	
Symptomatic congestive heart failure or asymptomatic left ventricular systolic dysfunction which persists for $\geq 4$ weeks	Permanently discontinue osimertinib
Electrocardiogram QT corrected (QTc) interval prolonged***	
Grade 1 (QTc 450-480 ms)	Maintain dose level
Grade 2 (QTc 481-500 ms)	
Grade 3 (QTc $\geq 501$ ms)	
 
Perform an analysis of serum potassium, magnesium, calcium, and phosphorus, and if below lower limit of normal, correct with supplements to within normal limits. Review concomitant medication uses for an agent which may cause prolonged QTc and discontinue if clinically feasible.
 
Hold osimertinib until QTc is less than 481 ms or to baseline if baseline is <math>>481</math> ms, then resume treatment, with osimertinib dose- if recovery within 3 weeks of onset, then restart at a reduced (40 mg) or at 80 mg (at the discretion of the investigator).* If QTc prolongation recurs patient will be permanently discontinued from the study.
 
Repeat ECG in 24 hours, or less, as clinically indicated; continue monitoring as clinically indicated until QTc <math><481</math> ms.
 
Repeat ECGs 7 days after dose resumption for all patients who had therapy interrupted due to QTc <math>\geq 501</math> ms.
 

Grade 4 (QTc $\geq 501$ or $>60$ ms change from baseline and Torsades de pointes or polymorphic ventricular tachycardia or signs/symptoms of serious arrhythmia)	Permanently discontinue patient from study
*Patients requiring a delay of $>2$ weeks should go off protocol therapy	
**Patients who do not tolerate dose level -1 dosing should go off protocol therapy	
***QTc prolongation as confirmed on three separate ECGs	

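### Section 5.2 leaves the restart dose after a later interruption to the Investigator, against fixed rows in Tables 5.4 to 5.6, and no text says which rule prevails

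*Combined protocol and SAP*

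**What the plan says.** Section 5.2 treats interruptions in two steps. For toxicity of grade 3 or higher, or otherwise unacceptable, "dosing will be interrupted and supportive therapy administered as required in accordance with local practice/guidelines". If it settles within 3 weeks, the first restart is at 80 mg or 40 mg under the rules that follow (Table 5.2 is named) and with the PI's agreement. The closing paragraph covers an event that later requires interruption: "osimertinib may restart at the same dose or the reduced dose, on resolution/improvement of the AE at the discretion of the Investigator". That paragraph names no table, grade or type of event.

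The text after Table 5.2 introduces the tables with "The following dose modification rules will be used with respect to potential toxicity". They then differ in how much choice they leave:

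- Table 5.3 (general events), grade 3: "Resume at one dose level lower, if indicated". Grade 4 ends protocol therapy.
- Table 5.4 (diarrhea), grade 3: "Resume at one dose level lower", with no qualifier. Grade 4 ends protocol therapy. A footnote adds: "Patients who do not tolerate 40 mg PO daily dose will be taken off protocol therapy".
- Table 5.5 (QTc): a first grade 3 event may restart at 40 mg or 80 mg at the Investigator's choice, but "If QTc prolongation recurs patient will be permanently discontinued from the study". Grade 4 QTc events and ILD of any grade also mean permanent discontinuation.
- Table 5.6 (skin), grades 3 and 4: one level lower, with no qualifier.

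**The concern.** The closing paragraph of Section 5.2 loosens control just when a patient has shown toxicity more than once. A site that applies it as written could re-expose a patient with recurrent QTc prolongation whom Table 5.5 stops. It could also keep on 80 mg a patient whom Table 5.4 or 5.6 reduces to 40 mg. These patients are waiting for planned resection, and the trial runs at several sites, so sites should not have to work out for themselves which instruction wins. What is at stake is consistent safety management, not the efficacy result.

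**Working it through.** The plan gives no figure for this point. The check sets the texts side by side and then sizes the problem.

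**1. Case by case, at a later interruption**

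| Situation | Section 5.2, closing paragraph | Table | Result |
|---|---|---|---|
| QTc prolongation recurs after a grade 3 event | Restart allowed | 5.5: permanent discontinuation | Conflict |
| Grade 3 diarrhea on 80 mg | 80 or 40 mg | 5.4: 40 mg | Conflict at 80 mg |
| Grade 3-4 skin event on 80 mg | 80 or 40 mg | 5.6: 40 mg | Conflict at 80 mg |
| Grade 4 diarrhea; grade 4 general event | Restart allowed, read literally | 5.4, 5.3: therapy ends | Conflict, read literally |
| Grade 4 QTc; ILD of any grade | Restart allowed, read literally | 5.5: permanent discontinuation | Conflict, read literally; for ILD, Section 5.3.1 repeats the stop |
| First grade 3 QTc event | 80 or 40 mg | 5.5: 80 or 40 mg | Agree |
| Grade 3 general event on 80 mg | 80 or 40 mg | 5.3: lower if indicated | Agree |
| Repeat event on 40 mg | 40 mg again | 5.3-5.6: therapy ends if 40 mg is not tolerated | Open: *not tolerated* is undefined |

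A patient can be on 80 mg at a second interruption because Section 5.2 allows a first restart at 80 mg, and the grade 2 rows of Tables 5.3 and 5.4 resume at the same dose.

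**2. Does any text settle precedence?** The sentence after Table 5.2 says that the rules will be used, but does not mention the discretion just granted. Section 5.3 adjusts dose to the system with the greatest toxicity, which chooses between concurrent toxicities, not between rules. Section 5.3.1 (Prolonged QTc) describes Table 5.5 as recommendations. Two pointers do not help: Table 5.2 lists only the 80 mg and 40 mg levels, and Section 5.3 sends the reader to Section 6.2, which covers specimens.

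**3. Hold limits.** Section 5.2 allows 3 weeks. The text after Table 5.2 and the footnotes to Tables 5.3-5.6 allow 2 weeks. The QTc row of Table 5.5 says 3 weeks above a 2-week footnote, and Section 5.3.1 says 21 days. Making the tables govern would therefore leave Table 5.5 at odds with itself.

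**4. Frequency.** Inputs: 27 patients (Section 3.2) and the grade 3 or higher rates in Table 4.4.

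- Diarrhea: 27 × 0.010 = 0.270
- Rash: 27 × 0.007 = 0.189
- QTc: 27 × 0.007 = 0.189
- Sum: 27 × 0.024 = 0.648

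The conflict also needs a second interruption or a recurrence. If a fraction *f* of these patients has one, the expected number is 0.648 × *f*. As an assumption only, *f* = 0.1 gives 0.065 and *f* = 0.5 gives 0.324. The ceiling, at *f* = 1, is 0.648. Grade 4 general events are outside this count, because Table 4.4 does not separate grade 4 from grade 3.

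**5. Dosing time left.** Section 3.4 bars Cycle 2 after a grade 3 or higher event in Cycle 1. The nominal last dose is then day 28 + 14 − 3 = 39, or day 31 + 14 − 3 = 42 with the 3-day visit window of Section 6.1. If the Cycle 1 interruption was below grade 3, Cycle 2 stays open and the nominal last dose is day 56 + 14 − 3 = 67.

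**The case against.** The best defence is that permission is not contradiction. Section 5.2 says that the drug *may* restart, while the tables are introduced as rules that will be used. A site can satisfy both by stopping for recurrent QTc prolongation and by choosing 40 mg after grade 3 diarrhea or a severe skin event. The headings also separate general from specific adverse events, which explains why grade 4 skin events are handled differently in Table 5.6 than in Table 5.3. Section 5.3 asks that management of any grade 3 or higher toxicity be discussed with the PI, and Section 8.2 provides continuous safety review by the PI and the DSMC.

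Most of this stands. It makes the tables the likely intent and lowers the practical risk. It does not remove the discretion that Section 5.2 grants without limit, and no sentence says that the tables override it.

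A reader might infer that the plan directs sites to re-challenge after recurrent QTc prolongation, or that PI control disappears after the first restart. The documents support neither: the sentence only permits a restart, and Section 5.3 still calls for PI discussion. A reader might also count a repeat event on 40 mg as a definite conflict. That depends on whether one repeat amounts to not tolerating 40 mg, which the protocol does not define.

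**Conclusion.** The text is wrong as written, but the matter is a minor patient-safety inconsistency. The firm conflicts are with Table 5.5 on recurrent QTc prolongation and with Tables 5.4 and 5.6 on the dose after grade 3 diarrhea or grade 3-4 skin events. On a literal reading the sentence also reaches rows that end therapy, so a short closed list of affected cases would be misleading.

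About 0.65 of 27 patients would have any grade 3 or higher diarrhea, rash or QTc event, and fewer would reach a conflict. This assumes that the Table 4.4 rates add and carry over to this trial. They come from the AURA studies, and treatment here lasts at most about 70 days, so they may overstate the number. A reader might want a percentage chance of at least one affected patient, or a firm limit on the remaining days of dosing. The documents support neither: they give no recurrence rate, and the day-39 limit does not apply when the first grade 3 event falls in Cycle 2. The MPR definition, its analysis and the power for 27 patients are unaffected.

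**What to change.** Amend the wording as follows.

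- **Section 5.2:** state that restart dose and discontinuation after any interruption, first or later, follow Tables 5.3-5.7; that the event-specific table overrides Table 5.3 and the general text; and that Investigator discretion applies only where a row grants it (Table 5.3 grade 3, the first grade 3 QTc event in Table 5.5, and footnote c of Table 5.7).
- **40 mg:** state that an event requiring dose reduction in a patient already on 40 mg ends protocol therapy. This also closes the gap left by the undefined term.
- **Hold limit:** use one maximum, for example the 2 weeks in the text after Table 5.2 and in the table footnotes, in place of the 3 weeks or 21 days in Section 5.2, Table 5.5 and Section 5.3.1 (Prolonged QTc).
- **Section 5.3:** replace the pointer to Section 6.2 with Sections 5.2 and 5.3.1.

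The cost is an amendment and slightly less Investigator discretion. With a 2-week limit, a patient who recovers between weeks 2 and 3 would leave protocol therapy. Sample size and analysis do not change.
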